Stage 2: Data will be collected from focus groups of eye care professionals, family carers and professional (paid) carers and interviews with people with dementia. The focus group question schedule will be semi structured and cover participants' understanding of eye care for people with dementia; expectations of the eye examination; experience of eye examination and eye care of people with dementia; barriers encountered; and facilitators and strategies to improve eye care. Data obtained in each interview will depend on the individual's ability to recall, communicate and comprehend and will vary according to the degree of dementia.

Data analysis

Stage 1 – prevalence, along with their 95% confidence intervals, of VI due to refractive error, cataract, age-related macular degeneration, glaucoma and diabetic retinopathy will be established. These Confidence Intervals will be used to compare the prevalence of the VIs with published figures in the general population. Prevalence levels between people living at home and people living in care homes will be compared using tests for two independent proportions. Proportions of both previously undetected cases and detected but inappropriately managed cases will also be compared between people living at home and in care homes.

Missing data:

Our primary research objective was to measure the prevalence of a range of vision problems in a generic sample of people with dementia aged 60 to 89 years. The study is adequately powered to achieve this objective. The use of two groups of subjects is mainly to allow us to identify any differences in the level of undetected or inappropriately managed visual impairment between the two groups. This will inform Stage 2 of our study, in which we will investigate the reasons for any undetected or inappropriately managed visual impairment.

Our sample size of 385 subjects in each group is based on an estimated prevalence of 50% with 5% precision and 95% confidence. This figure of 50% was the highest prevalence quoted in the literature for one of our target conditions. If the prevalence of a condition is either greater than or less than 50% then the study will require a sample size smaller than 385. We had anticipated that in a study of this nature there would be some missing data for each of the optometric tests as some of the participants/patients will be unable to perform them. There is no published data on the percentage of those with dementia who will be able to perform successfully individual elements of an eye examination. In the absence of published data we

took the view when writing our proposal that even if as few as 50% of subjects were able to complete a particular test with a prevalence of 50% (the worst case analysis) we would still have data from 385 subjects (50% of our total of 770), which is sufficient to generate a reliable estimate of the overall prevalence for the condition in a generic sample of patients with dementia.

Following the request for more detail on the impact of missing data we have consulted with a number of optometrists with extensive experience of eye examinations conducted on patients with dementia. Based on their responses we have quoted in Section 2 above (Testing people with dementia) estimates for the percentage of patients with dementia who are likely to be able to complete each test. The lowest percentage they estimate is 60%, compared with our worst case figure of 50% which was the figure used for our sample size calculation. Furthermore, these estimates suggest that, not only does our study have sufficient power to be able to generate a reliable generic figure for prevalence in dementia for each of our target conditions, but also that we should have sample sizes that are sufficiently large to allow statistical testing of differences in prevalence between our two groups (care home residents versus those living at home) for at least two thirds of the target conditions.

In the absence of published data on the likelihood of a patient with dementia being able to complete each of the tests comprising a full eye examination, an important secondary outcome of our study will be the determination and dissemination of estimates for the percentages of patients with dementia likely to be able to perform each test successfully. The data that we plan to collect beyond that derived from the eye examination (Carer data/ responses; Activities of Daly Living data; Quality of Life data etc.) will provide valuable information for the study, and these data will be gained even from participants who are unable to complete the eye examination – and may be particularly useful to have for this group. Understanding (and having evidence of) which elements of vision testing and eye health examinations are problematic and some of the characteristics of the individuals for whom these elements of an over all eye examinations are more likely to be difficult is an important piece of information in itself.

Stage 2 – Data collected in the focus groups and interviews will be audio recorded and the recordings will be transcribed. The transcripts will be analysed using Framework Analysis (29) to identify recurring themes. These themes will include, but not be limited to, experiences of eye care, reasons for under-detection and inappropriate management of VI, and recommendations for practice and future research. Data analysis will be undertaken independently by two of the research team, then compared for inter rater reliability.

Contribution to collective research effort and research utilisation

Prior to publication of the summary report, the findings and recommendations will be circulated to stakeholders, including participants in Stage 2 focus groups, for review and their contributions. Following publication of the summary report, papers will be submitted for publication in relevant professional and peer reviewed journals.

The College of Optometrists will use the study findings to update its guide lines on examining people with dementia (2). The College will also incorporate the findings into its programme for continuing education and training of optometrists.

The Alzheimer's Society and Thomas Pocklington Trust will disseminate the study findings through their networks and on their websites, and will develop guidelines for people with dementia, carers and health care professionals.

Pocklington is committed to the dissemination of research findings and their translation into forms that can affect policy and practice. We make findings freely available through publications, training and workshops. Our publications routinely reach over 2000 people / organisations involved in research, policy and practice affecting people with sight loss.

Both Pocklington and Alzheimer's Society are members of the Vision 2020 UK Dementia and Sight Loss Interest Group and can use its contact with policy makers and practitioners to promote and disseminate findings.

Plan of investigation and timetable

April - September 2012 : (between notification of successful application and study start date)

- Advertise and appoint the Project Manager, Researcher and Research Administrator
- Confirm Research Sites and Principal Investigators at research sites through DeNDRoN LRNs and CLRNs
- Design Participant Information material, consent forms and data collection forms
- Apply for and secure NHS Ethical approval
- Apply for NHS permissions using NIHR CSP (Coordinated System for gaining NHS Permission)
- Identify and recruit research optometrists

N.B. This work will be carried out by the Lead Applicant using College of Optometrists' resources and co-applicants' support as detailed in the application.

October 2012 - April2014: Stage 1

- October 2012: train research optometrists
- November 2012: pilot procedures
- January December 2013 recruit subjects and data collection
- January April 2013: data analysis

February 2013 - 2 - April 2014: Stage 2

- February 2013: arrange focus group dates and venues
- March September 2013: recruit participants for Carer focus groups
- June September 2013: recruit participants for Eye Care Professionals' focus groups
- October November 2013: run focus groups (x 12)
- March November 2013: recruit and conduct interviews with people with dementia (x30)
- November 2013 April 2014; focus group and interview data analysis

May – September 2014: reporting and dissemination

Approval by ethics committees

Ethical approval will be sought through the NHS Research Ethics process. Site specific NHS R&D approval will be required at all sites involved in recruiting subjects. Application will be made via the NIHR Coordinated Systems for gaining NHS Permission facilitated through DeNDRoN.

Project Management

[name] (MB), Lead Applicant and Director of Research at the College of Optometrists will have overall management responsibility for the project. He will line manage the Project Manager, Researcher, Administrator and College staff involved in supporting the study.

A Management Group will be established to operationalise the study and ensure that the project progresses according to the proposal. The Management Group will comprise MB, the Project Manager, Researcher, [name] (DE) and [name] (BH). DE will lead on the Stage 1 prevalence study and BH will lead on the Stage 2 qualitative study.

The Management Group will report to a Steering Group comprised of all project applicants, the Project Manager, Researcher, additional service user representatives and one of the research optometrists collecting data in Stage 1. The Steering Group will meet six times a year and communicate via email in-between meetings to oversee the project and provide ongoing advice to the Management Group.

The Project Manager and Researcher will be responsible for liaising with Principal Investigators (PIs) at research sites, recruiting subjects and optometrists who will collect data in Stage 1. The composition of the Steering Group is such that at least one member has preexisting links with each of the areas proposed, and one member of the Steering Group will have a role supporting the Project Manager and Researcher in each of the four geographic areas.

Public contributor/public involvement

This project has benefitted from public involvement from its genesis. It was presented at a workshop facilitated by the Alzheimer's Society on May 5th 2011, a workshop specifically organised to provide public involvement in research. 40 volunteers attended the meeting and 9 groups of volunteers had expressed an interest in the project based on reading the original abstract. All groups were strongly supportive of our research proposal. Public involvement will continue throughout the project.

The aims of active involvement in the project are:

- Ensuring that the research topic is relevant to the experiences and needs of carers and patients
- Ensuring that the outcomes measured are appropriate to carers and patients
- To benefit at all stages of the project from the perspective of carers and patients
- Contributing to development of Participant Information materials thereby assisting with recruitment of subjects
- Improve the relevance of results and recommendations

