Generalisable findings and prospects for change: The study will produce generalisable findings by collecting data from a sample from four centres in England selected to ensure a mixture of city, urban and rural settings and to encourage inclusion of people from a range of black and minority ethnic populations. This will ensure that the findings are of value to the NHS management community and NHS commissioners throughout England. The study will offer a number of recommendations on improving access to, and the quality of, eye examinations for people with dementia. However, individual stakeholder organisations may decide to focus on specific recommendations that will complement existing services, in the same way that enhanced eye care services for other patient groups have started to be implemented in recent years. For example, as in the case of people with learning disabilities, commissioners variously decide to focus on training progammes for optometrists to improve their skills in working with people with dementia, or to fund an enhanced fee (over the normal GOS fee) to cover the cost of extended appointment times, or to review the provision of domiciliary services. In our pilot investigations we found that among family carers of people with dementia there was limited awareness of either the entitlement to domiciliary services or the means of accessing them. We also found some accounts that this information was difficult to get from PCTs (which contracted these services at the time) and Optometrists (who are contractually obliged to either provide such services or offer clear information about how such services can be accessed).

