The Stage 1 cross sectional study will investigate two groups of people with dementia aged 60-89 years with 385 people in each group. Group 1 will comprise people living at home and Group 2 will comprise people living in care homes. The sample size has been calculated to allow detection of a prevalence of 50% with 5% precision and 95% confidence based on the reported estimated prevalence of VI in the population (5, 26). Subjects will be recruited through Memory Clinics and Old Age Psychiatry clinics in NHS trusts and through general medical practices with the assistance of DeNDRoN and Local Coordinating Research Networks. Additionally, Group 1 subjects will be recruited through Alzheimers Society local groups and Group 2 subjects will be recruited through direct contact with care homes. Where participants are recruited via AS, they will only be recruited from groups of service users for whom a medical diagnosis of dementia has been confirmed through the AS processes. It should also be noted that recruitment through AS is not intended to be the primary route, but rather an additional source of participants to enhance the overall recruitment strategy. BUPA

has offered to support the study but we will also recruit through other care providers to reduce the risk of selection bias. Further subjects for both groups, especially those living at home, can also be recruited through The Outside Clinic, one of the UK's leading providers of domiciliary eye care services. They have informed us that they test approximately 2,500 people with dementia each year (living in their own homes and in care homes).

Strategy: The team is aware that recruitment of people with dementia into research studies is not easy and we have adopted a multilayered approach to recruitment. It is intended that the majority of subjects for the prevalence study will be recruited with the assistance of regional DeNDRoNs and CLRNs.

DeNDRoN is launching the ENRICH research ready-care home network this year and we will make use of this to recruit participants.

Identification procedures

Potential participants with dementia will be identified from their medical records by the direct care team or by DeNDRoN or Local Coordinating Research staff who are frequently embedded in NHS clinics. In addition DeNDRoN maintain case registers of patients with dementia who are willing to participate in research and suitable participants who are on this register will be identified and approached.

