Other methods of recruitment will involve posters and notices in NHS clinical areas informing patients that the study is being conducted and giving contact details. Similarly potential patients will be recruited via the Alzheimer's Society; however this recruitment process is external to NHS clinics and thus we will, with written consent from potential dementia participants approach their general practitioner to clarify from their medical records that they meet eligibility for inclusion in the study (e.g. a formal diagnosis of dementia).

We have identified a possibility that a small proportion of the potential participants may already be participating in clinical trials for new pharmaceutical products. As there would be no information about potential interactions between the trial drug and other medications or drugs used during the eye examination (i.e. Tropicamide), we will exclude patients on such trials from this study.

Given that the study requires carer/family member involvement at a number of stages, we will seek to involve only those patients with dementia who have carers or family members. Identification of carers / family members will proceed in tandem with the identification of suitable dementia participants; details of carers / family members are frequently recorded in both primary and secondary care medical records and in DeNDRoN associated patient case registers.

Approach and consent procedures

The initial approach will either be made by direct care team or a member of the DeNDRoN to appraise the participant as well as family members/carers of the study and its remit. This will either be done by direct face to face (for example in clinic), telephone or letter. Participants and family members/carers will then be provided with written information on the study's purpose, methods, risks and burdens, and given a minimum of one week to consider their participation.

Subsequent to this participants and family members/carers will then be contacted by either a DeNDRoN staff member or by a member of the research team (either face to face or by telephone depending on the participant's preference) to determine if a participant and family member/carer is willing be involved in the study. Formal written consent will either be sought then from the patient or just prior to the formal study assessments. In addition, given the involvement of carers / family members in the study (for example carer's views) separate

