Additionally, individual face-to-face interviews will be sought with people with dementia who are able to consent to interview. Interviews will continue until no new data is being generated. Qualitative studies usually achieve saturation with 30 subjects (28) and this is the number envisaged in this study although recruitment will continue beyond 30 subjects if necessary.

Setting/ context

In Stage 1, subjects will be randomly recruited from multiple sites in four centres in England: London, Thames Valley, East Anglia and the North East to reflect demographic differences such as city, urban and rural settings and to encourage inclusion of people from a range of black and minority ethnic populations. We will recruit from multiple sites within each region. Regional Network Coordinators were contacted at the proposal development stage; they did an initial canvas for support which revealed widespread interest from local PIs and feedback that the study would be likely to be popular with patients and carers given the practical and widespread applicability of the topic.

Difficulties in recruiting people from black and minority ethnic groups were addressed in feedback to reviewers following submission of the full proposal. Our strategy aims to recruit subjects from a range of geographic areas to include a demographic mix of inner city, urban and rural areas. We will purposely seek to recruit subjects from BME groups in city populations where the ethnic populations are greatest e.g. London (North Thames), Leicester (Thames Valley). We have also approached the Primary Care Research Network in Central England (PCRN-CE) which has offered to approach GPs across their area to identify BME patients who could be invited to participate in the study.

The Stage 2 focus groups and individual face-to-face interviews with people with dementia will also be held in the same four centres.

Data collection

Stage 1: The subject will have a full optometric examination in line with requirements of the GOS sight test for people aged 60 years and over and the College of Optometrists' guideline CO4: *Examining the patient with dementia or other acquired cognitive impairment*.

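### Stage 1 is described as random recruitment, but every route is convenience or purposive, so the prevalence estimates and the generalisability claim lack their stated basis

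*Protocol*

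**What the plan says.** The Setting/ context section states the selection method for Stage 1: "In Stage 1, subjects will be randomly recruited from multiple sites in four centres in England". In the same section the sponsor adds "We will purposely seek to recruit subjects from BME groups in city populations where the ethnic populations are greatest", and reports that a Central England primary care network "has offered to approach GPs across their area to identify BME patients who could be invited to participate in the study". Central England is not one of the four named centres.

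The Sampling section and its Identification procedures describe the routes in practice. The main one is network support: "It is intended that the majority of subjects for the prevalence study will be recruited with the assistance of regional DeNDRoNs and CLRNs". Candidates are found in medical records by care teams or network staff. Beyond that, "DeNDRoN maintain case registers of patients with dementia who are willing to participate in research", and people on those registers will be approached. "Other methods of recruitment will involve posters and notices in NHS clinical areas" as well. Further routes are Alzheimer's Society groups, direct contact with care homes, and a domiciliary eye care provider that tests about 2,500 people with dementia a year. Only patients with a carer or family member are sought.

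On the reach of the results, the paragraph on generalisable findings in the Need section says "The study will produce generalisable findings by collecting data from a sample from four centres in England" and expects them to be useful to commissioners across England. The Data analysis section plans prevalences with 95% confidence intervals and uses those intervals for comparison with published general-population figures.

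**The concern.** Prevalence is the primary objective, and the second objective is a comparison with external figures. Both depend on how the participants came to be in the sample. If selection is random from a defined population, the observed proportion estimates that population's prevalence and the interval covers it at the stated rate. If selection is by convenience, the proportion estimates prevalence among whoever was reached and agreed. The interval then measures only sampling noise around that quantity.

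One route deserves particular attention. Clients of a domiciliary eye care provider are already receiving eye care, whereas the Background section says that uptake of sight tests among people with dementia is thought to be considerably lower than among over-60s generally. This route is tied directly to the outcome of undetected or inappropriately managed impairment. The protocol says it can supply both groups, especially people living at home, so it may also load unequally on the home versus care home comparison.

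**Working it through.** **Step 1: the plan's own figure.** Inputs from the Sampling section: prevalence p = 0.50, precision d = 0.05, 95% confidence.

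n = z² p(1 − p) / d² = 1.95996² × 0.25 / 0.0025 = 384.15, rounded up to 385 per group.

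The figure reproduces. This is the formula for a simple random sample. The matching half-widths are 1.96 × √(0.25/385) = 4.99 points for one group and 1.96 × √(0.25/770) = 3.53 points for the total of 770.

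**Step 2: is there a random draw?** Each route set against the stated method:

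- Identification from records by care teams or network staff, then invitation: no list is defined from which patients are drawn, and no rule says who is picked.
- Registers of people willing to join research: self-selected before the study starts.
- Posters and notices: self-referral.
- Alzheimer's Society groups: convenience, described as an additional source.
- Direct contact with care homes: no random selection of homes or residents is described.
- Domiciliary eye care provider: convenience, and linked to the outcome. Its yearly volume is 2,500/770 = 3.2 times the whole sample, and no cap on its share is stated.
- BME recruitment in cities and through the Central England network: purposive by its own description, with no quota or share stated.

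None of the seven is a probability sample. The protocol mentions selection bias only when explaining the use of more than one care home provider.

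**Step 3: what could be at stake.** The document gives neither the mix of routes nor how prevalence differs between them, so the following rests on assumptions. Let e be the share by which the sample over-represents some route or subgroup, and D the difference in prevalence between that part and the rest. Then:

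- bias b = e × D
- SE = √(0.25/770) = 1.80 points
- coverage = Φ(1.96 − b/SE) − Φ(−1.96 − b/SE)

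| e | D (points) | Bias (points) | Coverage of nominal 95% interval |
|---|---|---|---|
| 5% | 5 | 0.25 | 94.8% |
| 10% | 10 | 1.0 | 91% |
| 20% | 10 | 2.0 | 80% |
| 20% | 20 | 4.0 | 40% |

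The first row is negligible. In the last row the bias exceeds the half-width of 3.53 points. The sign of D is unknown, and a larger sample would not reduce the bias.

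**The case against.** The strongest case on the other side has four parts.

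**Recruitment is mostly by invitation.** Most participants are to come with network support, and identification from records followed by invitation is a stated method. The registers, posters and society groups are supplements. This stands: it would be wrong to call the sample simply volunteers. But invitation without a frame and a random draw is still convenience recruitment.

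**The BME effort may improve representativeness.** A reader might infer that targeted recruitment enriches the sample and inflates prevalence. The document does not support that. The effort is introduced as a response to difficulty in recruiting BME people, it has no quota, and it may only offset under-recruitment. Figures can be made to point either way. Take the Background's 3.3% for glaucoma (people over 70, general population) and assume a 5% BME population share and a prevalence ratio R of 2 to 3. Prevalence in the remaining population is 3.3/(0.95 + 0.05R), which is 3.14% for R = 2 and 3.00% for R = 3. With BME people as 10% of the sample and R = 2, the pooled figure is 3.14 × 1.10 = 3.5%. With 20% and R = 3 it is 3.00 × 1.40 = 4.2%. With none recruited it falls to 3.0–3.1%. The share and ratio are not in the document. All these shifts also lie within the random half-width of 1.96 × √(0.033 × 0.967/655) = 1.4 points at 85% completion of 770. Removing the purposively recruited participants could make matters worse.

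**Weighting and sensitivity analyses belong in an analysis plan.** That plan may exist and was not available here, so their absence from the protocol is not the finding. No analysis plan, however, can make the word random true of this recruitment.

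**The sponsor took sensible steps.** It uses several care providers, many sites in four regions, and includes people who lack capacity. The remark about commissioners across England concerns usefulness rather than representativeness. These points soften the criticism, but the sentence promising generalisable findings remains unqualified.

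**Conclusion.** Wrong as written, and worth correcting. The protocol claims random recruitment and describes only convenience and purposive routes. The prevalence estimates, the intervals used against general-population figures and the generalisability claim therefore lack the random-sample basis stated for them.

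The textual contradiction needs no assumptions. The size and direction of any bias cannot be derived from the document: the illustrations run from no practical effect to a bias larger than the half-width, on assumed inputs. The sample size arithmetic is not at fault. Nor is convenience recruitment a fault in itself, since it may be the only feasible approach in this population.

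Two stronger conclusions might tempt a reader: that BME enrichment biases the pooled prevalence upward, and that the results cannot be used. Neither follows from the text.

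**What to change.** - **Setting/ context:** replace the statement of random recruitment with the convenience and purposive methods actually planned.
- **Need, paragraph on generalisable findings:** limit the claim to what such a sample supports.
- **Data collection:** record each participant's recruitment route and ethnicity at enrolment, because route may not be recoverable later.
- **Data analysis:** report prevalence by recruitment route as a sensitivity analysis, in particular with and without participants from the domiciliary eye care provider. Standardise to a stated reference population where its composition is available.
- **Keep** the purposively recruited BME participants in the main estimate.

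The cost is some rewording, two coded variables, a little extra analysis and a more modest claim. Estimates for small routes will be imprecise and should be presented as descriptive.
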